3.3 Inclusion Criteria

1. Male and female subjects aged 55-79 years
2. Current or former smokers
3. Subjects with calculated risk score PLCO₂₀₁₂ $\geq 1.58\%$ (6 yrs.) or NELSON inclusion criteria (current or former smokers [those who had quit ≤ 10 years ago] who had smoked > 15 cigarettes a day for > 25 years or > 10 cigarettes a day for > 30 years).
4. Able and willing to give written informed consent

Volunteers fulfilling all inclusion criteria are undergoing two low dose CT screening rounds (**high-risk group**).

In addition, non-qualifying subjects fulfilling inclusion criteria 1 (age), 2 (smoking history) and 4 (consent), but do not meet the inclusion criterion 3 (risk too low) will be asked to volunteer by contributing long-term outcome data informing of the development of lung cancer or death from lung cancer (n=7100 randomly selected, **low-risk group**). These subjects will be contacted via mail after a minimum of 5 year follow up to inquire if they developed lung cancer in the time between their recruitment and present. Non-responders will be followed by local registries and by phone. New lung cancer cases will be verified using official hospital or cancer registry documents. The 5 year follow up period was chosen to account for the lead-time bias between tumor and symptoms occurrence and cancer diagnosis in the low-risk group.

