3.4 Exclusion Criteria

1. Comorbidity, which would unequivocally contraindicate either screening or treatment if lung cancer were detected.
2. History of chest CT within the past year preceding the invitation.
3. Inability to undergo non-contrast CT (e.g. ≥ 200 kg body weight, inability to lie flat).
4. Pregnancy
5. Risk of non-compliance with study procedures.
 - Unable to give written consent

- Patient's inability to fill in the questionnaire self-dependent
- Limited knowledge of the German language
- Inability to travel, residents of care facilities, etc.

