5. STATISTICAL ANALYSIS PLAN

5.1 Statistical Methods – General Aspects

5.1.1 Primary and key-secondary Objective(s):

The primary and key-secondary endpoints of this study will be calculated from the following two fourfold tables summarizing the distribution of included patients and patients with detected lung cancer:

Table 1

Number of Participants by Screening Eligibility			
		NELSON	
		+	-
PLCO _{m2012}	+	A	B
	-	C	D*

Table 2

Number of detected lung cancers by Screening Eligibility			
		NELSON	
		+	-
PLCO _{m2012}	+	a	b
	-	c	d*

Please note that * indicates patients with a low risk score, which are both PLCO and LLP negative at inclusion.

PPV

PPV NELSON = $(a+c) / (A+C)$; PPV PLCO = $(a+b) / (A+B)$.

Proportion of lung cancer detected

Secondarily, proportion of lung cancers detected will be calculated as $\text{prop_lung(PLCO)} = (a+b) / (a+b+c+d^*)$ and $\text{prop_lung(NELSON)} = (a+c) / (a+b+c+d^*)$.

Additionally, also the proportion of lung cancers detected in the identified high-risk population (PLCO or NELSON positive) will be calculated, using $(a+b+c)$ as denominator and the proportion of individuals selected for screening within the low-risk population will also be calculated using $(A+B+C+D^*)$ as a denominator.

Proportion of individuals selected for screening

The proportion of individuals selected for screening (within the high-risk population) will be calculated as $\text{prop_screening(PLCO)} = (A+B) / (A+B+C)$ and $\text{prop_screening(NELSON)} = (A+C) / (A+B+C)$.

Specificity

Specificities of the risk scores will be calculated as $\text{spec(PLCO)} = (C+D^* - c-d) / (A+B+C+D^* - a - b - c - d^*)$ and $\text{spec(LLP)} = (B+D^* - b-d^*) / (A+B+C+D^* - a - b - c - d^*)$.

Sensitivity

The sensitivities correspond to the proportions of lung cancer detected in the overall population.

The primary and key-secondary endpoints will be compared between PLCO score and NELSON inclusion criteria in a hierarchical at a two-sided type-I-error of 5% to control the overall type-I-error at 5% (according to the hierarchy of endpoints outlined above). As the primary analysis, for testing the null-hypothesis of no difference between the risk scores regarding the proportion of lung cancers detected, McNemar's Test will be used.

Statistical testing

For testing the null-hypothesis of equal positive predictive values, the weighted generalized score statistic developed by Kosinski et al. (20) will be used.

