6. STUDY CONDUCT AND REGULATORY DETAILS

6.1 Data Management

6.1.1 Study Flow Chart and Plan

* Follow-up schedule

LungRADS Categories:

- 1, 2: 1 year LDCT
- 3: 6 months LDCT; VDT assessment
- 4a: 3 months LDCT; VDT assessment
- 4b, X: MDT, tissue sampling depending on the probability of malignancy and comorbidities.

Figure 1: Flow diagram of the HANSE study.

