6.1.2 Procedures

Figure 2: Procedure workflow of the Hanse Study

1. Recruitment

- Population will be contacted by mail (address data of individuals in the age group obtained from local population registries) with an **individually tailored invitation letter** and response element (paper and website) to assess their overall qualification and willingness to participate. Additional recruitment efforts via local physicians (**GPs**), and via **public media** using the study website.

Age	
Gender	
Race/ethnicity	
Education	
Height	
Weight	
Chronic obstructive pulmonary disease (yes vs. no)	
Prior diagnosis of pneumonia (yes vs. no)	
Prior diagnosis of emphysema (yes vs. no)	
Prior diagnosis of bronchitis (yes vs. no)	
Prior diagnosis of tuberculosis (yes vs. no)	
Personal history of cancer (yes vs. no)	
Family history of lung cancer (yes vs. no)	
Early onset vs. late onset	
Smoking status (former=0, current=1)	
Former smoker (yes vs. no)	
Current smoker (yes vs. no)	
Smoking intensity (average cigarettes/day)	
Smoking duration (years)	
Smoking quit-time	
Chest CT within past year (yes vs. no)	
Pregnancy yes/no	
Any comorbidities (free text)	
Ability to travel to the screening center	

Table 5: Variables for risk scoring, applicable for PLCO model

- Initial eligibility assessment based on self-reported data (age, smoking history and parameters required for the NELSON inclusion criteria and PLCO scores, table 5) in return letter, based on individuals' input in study website, or according to GP assessment. Data of eligible subjects will be stored in CRO database. Eligible subjects (based on initial assessment of risk) will receive an invitation for participation in the screening program with additional background information.
- On site validation of variables required for risk scoring models and accompanying assessment of medical condition, medical history, current medication by qualified medical staff.
- Data will be stored in database (CRO) and PLCO_{M2012} risk score and NELSON inclusion criteria will be determined. Individuals with PLCO_{M2012} risk score $\geq 1.58\%$ (6 yrs.) or NELSON inclusion criteria will be included in the study.

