- **Assessment of smoking status:** Success of the smoking cessation program will be evaluated using a questionnaire, combined with a urine cotinine check (in quitters).
- **Initiation of COPD treatment:** Assessment of COPD treatment initiation during the study.
- **Consequences of screening:** Questionnaire 'Consequences of Screening' as above.

2. Evaluation

Lung cancer screening:

- The percentage of subjects receiving an adequate low-dose CT scan according to DRG guidelines will be assessed.
- For all included participants, detection rate of lung cancers will be evaluated and categorized according to LungRADS 1.1 categories.
- Detected (proven by histopathology) lung cancers will be categorized whether they were predicted by PLCO or NELSON or both. Statistical analysis will reveal potential advantages of either risk scoring methodology.
- A retrospective analysis will compare this algorithm to the PanCan nodule algorithm vs. AI for management efficiency. Based on the two alternative management algorithms patients are sorted into three management groups: (a) next surveillance scan, (b) early recall scan, or (c) diagnostic evaluation recommended. For one algorithm to be more efficient, the following criteria must both be fulfilled
 - The number of patients without lung cancer sorted in the category (a) is higher AND
 - The number of patients with lung cancer sorted into category (b) or (c) is higher.

Coronary calcium score / cardio-vascular treatment initiation:

- At the 1-year follow-up visit, the rate of initiation of cardiovascular treatment (in particular lipid-lowering) will be determined, together with BMI, and blood pressure data. Data for the calcium score reporting group will be compared to those of the non-reporting group.

Smoking cessation:

- Success of smoking cessation counseling will be based on the number of participants quitting (% quitters) within study period.
- Allocation of the participants to the different experimental groups will allow determining the influence of 'reporting' of prognostic markers (percent emphysema and coronary calcium score) on smoking cessation.

All methods will be performed according to study site SOPs.

CT analysis software (Coreline) specifications:

1. Viewer function

- LCS (Lung Cancer Screening) viewer functions

- Image display with axial, sagittal and coronal images and 3D rendering.
- Virtual slice thickness control display function for MPR (Multi-Planar Reformat) images.

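### Screened cancers count only with tissue proof, low-risk cancers count from hospital or registry documents, and the 5-year proportion detected and sensitivity add the two together

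*Protocol*

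**What the plan says.** Three places in the protocol decide which cancers are counted.

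- **Screened high-risk group (cells a, b, c).** Section 6.1.2, Evaluation: "Detected (proven by histopathology) lung cancers will be categorized" according to which selection rule, or both, picked out the participant. For LungRADS 4b and X findings, the follow-up schedule in 6.1.1 reads "MDT, tissue sampling depending on the probability of malignancy and comorbidities". The protocol therefore expects that some suspicious findings will not be sampled. It gives no rule for a cancer that is diagnosed or treated without tissue.
- **Unscreened low-risk group (cell d\*).** Section 3.3, repeated in the synopsis: "New lung cancer cases will be verified using official hospital or cancer registry documents". Histology is not named.
- **How the cells are combined.** Section 5.1.1 sets the proportion of cancers detected to (a+b)/(a+b+c+d\*) for PLCO and (a+c)/(a+b+c+d\*) for NELSON, and equates sensitivity with these proportions. Specificity also uses all four cells. The synopsis and 4.2 place these endpoints at 5 years. The primary PPVs are (a+b)/(A+B) and (a+c)/(A+C).

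The limitations text after 5.2.2 acknowledges that clinically silent cancers in the low-risk group will be missed. It does not mention the difference in verification.

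**The concern.** Sensitivity needs the same meaning of a case in numerator and denominator. Here the cancers a rule can claim (a, b, c) must have tissue, while the cancers that both rules miss (d\*) need only be documented. If some high-risk cancers never yield tissue, the numerator shrinks by the full loss. The denominator shrinks by less, because d\* is held to a looser standard. The reported share of cancers caught is then too low for reasons unrelated to the selection rules. These are hierarchically tested key-secondary endpoints, and their absolute values are what a programme planner would quote.

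**Working it through.** **Inputs.** Predicted 5-year cancers in Table 3 (Protocol 5.3): a = 112.2, b = 27.0 (PLCO only), c = 9.8 (NELSON only), d\* = 21.8. Participants: A = 2857.04, B = 1072.73, C = 1070.25, D\* = 7095.8. The proportion q of high-risk cancers with tissue proof is not given in the protocol, so it is assumed and varied. d\* is taken as complete.

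**1. The plan's own figures.**
- Expected CT-detected cases: 34 × 5000/2029 × 1.72 = 144.1 (stated 144).
- PPV ratio: (139.2/3929.77)/(122.0/3927.29) = 1.140 (stated 14% higher).
- Simulated power with the weighted generalized score statistic, 200,000 runs: 79.9% (stated 80.3%).

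All three reproduce.

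**2. Sensitivity with equal loss in a, b and c.**

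PLCO: q(a+b)/[q(a+b+c)+d\*]. NELSON: q(a+c)/[q(a+b+c)+d\*].

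| q | PLCO | NELSON | Difference (points) |
|---|---|---|---|
| 1.00 | 139.2/170.8 = 81.5% | 122.0/170.8 = 71.4% | 10.1 |
| 0.97 | 135.02/166.33 = 81.2% | 118.34/166.33 = 71.1% | 10.0 |
| 0.80 | 111.36/141.0 = 79.0% | 97.6/141.0 = 69.2% | 9.8 |

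Both values fall together: by about 0.3 points at 3% loss, and by 2.5 (PLCO) and 2.2 (NELSON) points at 20% loss. The difference between the rules hardly moves.

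**3. Specificity.** At q = 0.80 it changes from 68.2% to 68.1% (PLCO) and from 68.1% to 68.0% (NELSON), less than 0.2 points each.

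**4. Primary PPV.** Neither formula contains d\*. With equal loss, q multiplies both numerators and cancels in the ratio: q(a+b)/(A+B) divided by q(a+c)/(A+C) stays at 1.140. The mismatch between high-risk and low-risk verification therefore cannot reach the primary contrast.

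**5. Paired test of the proportion detected.** McNemar's test compares the discordant cells b and c. d\* is concordant (missed by both rules) and drops out. The mismatch affects the reported percentages and not the direction of this test.

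**The case against.** **The standards may differ less than the wording suggests.** Section 3.3 names a source of verification, not a diagnostic standard, and hospital or registry documents may contain histology. Proof by histopathology can also come from a resected tumour, so only cancers that never yield tissue are lost. Exclusion criterion 1 in 3.4 removes "Comorbidity, which would unequivocally contraindicate either screening or treatment if lung cancer were detected", which reduces non-biopsy for comorbidity without removing it. These points limit the size of the effect; they do not align the definitions.

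**The histology sentence may not govern the 5-year counts.** It stands in the evaluation that follows the two screening rounds. The protocol does not say how high-risk cancers arising after round 2 are ascertained or verified, so applying the sentence to them is an inference. That is correct, but the remaining gap needs the same repair.

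**A stronger reading: the rule disfavours PLCO in the primary comparison.** A reader might argue that COPD and related history enter the PLCO score and not the NELSON smoking rule. PLCO-only participants would then be biopsied less often and lose more cases. The contrast is sensitive to such a gap, because it rests on about 26 PLCO-only and 9 to 10 NELSON-only detected cancers. If 97% of cancers in the NELSON-positive cells were proven, against 90% or 85% in the PLCO-only cell, the PPV ratio would be 1.12 or 1.11 and power about 70% or 63%. The protocol gives no proof rate by cell, and the whole drop comes from that assumed gap. PLCO-only status can also arise from having quit more than 10 years ago, which says nothing about fitness for biopsy. The documents do not support the claim of bias.

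**A second stronger reading: both sensitivities must fall.** This holds for roughly equal loss only. Under the unequal rates just given, PLCO falls to 81.0% or 80.8%, but NELSON rises from 71.4% to 72.0% or 72.6%.

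**Conclusion.** The concern holds for the absolute 5-year proportion detected and sensitivity. As written, the plan adds cases verified to two different standards and gives no rule for a high-risk cancer without tissue. The effect is modest: with equal loss across a, b and c it runs from about 0.3 points at an assumed 3% loss to 2.2 to 2.5 points at an assumed 20%. It is negligible for specificity.

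These sizes rest on the Table 3 predictions, on d\* being fully counted, and on the histology rule applying to high-risk cancers up to year 5. They isolate this one mechanism. The missed silent cancers that the protocol already concedes would push sensitivity upward, so the net bias is not determined.

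The mismatch does not touch the primary PPV and by itself favours neither rule. An effect on the PPV contrast between the rules would need unequal tissue-proof rates in the PLCO-only and NELSON-only cells. The protocol gives no such rates, so that possibility is a reason to record and report them, not a demonstrated bias.

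**What to change.** **5-year endpoints.** State one case definition for all four cells, covering high-risk cancers that arise after round 2: histology or, where no tissue was obtained, a lung cancer documented by the tumour board, a hospital or the registry. Record the basis of diagnosis for every case.

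**Primary PPV.** Keep histology. Report the proof rate separately for the both-positive, PLCO-only and NELSON-only cells. Add a sensitivity analysis that also counts documented clinical diagnoses. This would show whether proof rates differ between the rules.

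**Cost.** A wording change, one eCRF field and one extra analysis. The field should be in place early, since the basis of diagnosis is hard to reconstruct later. The drawback is that a few cases of lower diagnostic certainty enter the 5-year counts. The change concerns outcome counting only; the clinical rule on tissue sampling stays as it is.
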